5.2. Analysis Methods

5.2.1. Patient Disposition

Summary of study disposition will be summarized by dose level and overall for Part 1 as well as by disease cohort and overall for Part 2:

Based on all subject set, the following will be summarized:

- Number of patients who signed the pre-screening informed consent
- Number of pre-screen failures and reason for pre-screen failures
- Number of patients who signed the informed consent
- Number of screen failures and reason for screen failure
- Number of patients enrolled
- Number of patients who do not receive study treatment
- Number of patients who received study treatment

Based on safety analysis set, the following will be summarized:

- Patients still on treatment
- Number and percentage of patients who discontinue the study drug
- Reason for study drug discontinuation (for study drug)
- Number of patients still on study
- Number and percentage of patients who discontinue the study
- Reasons for discontinuation of the study

A separate table will be presented to show the patients included in each analysis set and proper reasons for exclusion from an analysis set.

Patient's discontinuation and follow-up status and inclusion in analysis sets will be also listed.

5.2.2. Protocol Deviations

Protocol deviations will be summarized descriptively (frequency and percentage) for patients with any major protocol deviation, and by major protocol deviation categories. A patient with multiple protocol deviations under the same category will be counted once per deviation category. The protocol deviation summary is based on the safety analysis set.

In addition, all protocol deviations will be presented in a by-patient listing.

5.2.3. Demographic and Other Baseline Characteristics

For the safety analysis set, demographic and other baseline characteristics, such as age (years) at informed consent date, age groups (<65 years, \geq 65 years), gender, child bearing potential (if female), race, ethnicity, baseline height (cm), baseline weight (kg), baseline BMI (kg/m^2) calculated as baseline weight (kg)/ [baseline height (m)]², BMI category $<18.5 \text{ kg}/\text{m}^2$, ≥ 18.5 and $<24 \text{ kg}/\text{m}^2$, $\geq 24 \text{ kg}/\text{m}^2$), and baseline ECOG status, will be summarized and listed.

5.2.4. Disease Characteristics

Oncology history will be summarized descriptively on the safety analysis set for the following:

- Time since First Diagnosis of disease (months) = (date of first study treatment administration – date of first diagnosis of disease + 1)/30.4375

- IDH Mutation Status (local). It is derived based on the IDH mutation status collected on the CRF. That is, if the status of a patient contains “IDH1”, “Arg132”, “c.394C”, the status for the patient will be assigned “IDH1”; if the status of a patient contains “IDH2”, “Arg172”, “Arg140”, “c.419G”, “c.515G”, the status for the patient will be assigned “IDH2”; if the status of a patient contains any item for defining IDH1 and any item for defining IDH2, the status for the patient will be assigned “IDH1 and IDH2” indicating a dual mutation for the patient.
- IDH anti-cancer medication history (IDH pre-treated vs naïve): the status of receiving prior IDH anti-cancer medication is derived from the prior anti-cancer medications. That is, if a patient took any medication with the PT (upper case) or drug verbatim name (upper case) containing any of the terms “ENASIDENIB”, “IVOSIDENIB”, “OLUTASIDENIB” or “LY 3410738”, the patient will be classified as “Pre-treated”, otherwise, the category of “Naïve” will be assigned
- Oncology classification (AML, HR MDS, AITL)
- If AML:
 - AML type: if secondary AML, the related therapy
 - Time since initial AML diagnosis (months) = (date of first study treatment administration –initial date of AML diagnosis+ 1)/30.4375
 - AML Subtype by WHO 2016, and classification under each subtype (if applicable)
 - AML genetic risk stratification
- If MDS:
 - MDS type
 - Time since initial MDS diagnosis (months) = (date of first study treatment administration –initial date of MDS diagnosis+ 1)/30.4375
 - MDS Subtype by WHO 2016
 - IPSS-R Score Value and IPSS-R prognostic risk category
 - Cytogenetics Score
 - BM Blast %, Hemoglobin, Platelets, ANC
- If AITL:
 - AITL Subtype by WHO 2016
 - Time since initial AITL diagnosis (months) = (date of first study treatment administration –initial date of AITL diagnosis+ 1)/30.4375
 - Ann Arbor Staging at screening
 - B-symptoms present or not at screening
 - IPI Risk group
 - Have FDG-PET avid disease or not
 - Bone marrow involvement or not
- Anatomical location of Primary tumor

In addition, all disease characteristics and oncology history data will be presented in a by-patient listing.

5.2.5. Medical History

The conditions/diseases from medical history are those conditions/diseases that stopped prior to the study entry. Medical history will be coded to SOC and PT using MedDRA Version 27.1 or higher.

The number and percentage of patients with any past medical/surgical history within each SOC and PT will be provided on the safety analysis set. The analysis will be repeated for patients with on-going medical history.

A patient will only be counted once within a particular SOC (PT) even if he/she has multiple conditions/diseases in the same SOC (PT).

Each summary will be ordered by descending order of incidence of SOC according to total column and PT within each SOC. If the frequencies tie, an alphabetic order will be applied.

In addition, medical history data will be presented in a by- patient listing.

5.2.6. Prior and Subsequent Anti-cancer Therapy

Prior and subsequent anti-cancer therapy, including mediation, radiotherapy, and procedure or surgery, will be summarized descriptively separately for the safety analysis set.

Prior anti-cancer therapy overview

- Medication
 - Patients with at least one prior anti-cancer medication
 - Highest line of therapy (descriptive statistics)
 - Intent
 - Reason for treatment discontinuation
 - Best response for AML, MDS, AITL
 - Had disease progression or not
- Radiotherapy
 - Patients with at least one prior anti-cancer radiotherapy
 - Anatomical Site
 - Purpose
- Procedures / Surgeries
 - Patients with at least one prior anti-cancer procedures/surgeries
 - If this procedure is stem cell transplant, type of stem cell transplant

Subsequent anti-cancer therapy overview

- Medication: patients with at least one subsequent anti-cancer medication
- Radiotherapy: patients with at least one subsequent anti-cancer radiotherapy
- Procedures / Surgeries:
 - Patients with at least one subsequent anti-cancer procedures/surgeries
 - If this procedure is stem cell transplant, type of stem cell transplant

5.2.6.1. Anti-cancer Medication

Prior anti-cancer medications are defined as those taken by the patient prior to the administration of study drug. Subsequent anti-cancer medications are defined as those taken by the patient after the discontinuation of the study drug.

In addition to the overview summary, prior and subsequent anti-cancer medications are coded to Anatomical Therapeutic Classification (ATC) therapeutic group (i.e. ATC Level 2) and PT using the World Health Organization Drug Dictionary (WHO-DD) Version September 2024 or higher.

The prior anti-cancer medications will be summarized by presenting the number and percentage of patients by ATC and PT. Patients taking the same medication multiple times will only be counted once for that PT or ATC. Each summary will be ordered by descending order of incidence of ATC and PT within each ATC. If the frequencies tie, an alphabetic order will be applied.

Similarly, the subsequent anti-cancer medications will be summarized by ATC and PT.

All prior and subsequent anti-cancer medications will be presented in a by-patient listing.

5.2.6.2. Anti-cancer Radiotherapy

Prior anti-cancer radiotherapy is defined as those taken by the patient prior to the administration of study drug.

Subsequent anti-cancer radiotherapy is defined as those taken by the patient after the discontinuation of the study drug.

In addition to the overview summary, all prior and subsequent anti-cancer radiotherapy will be presented in a by-patient listing.

5.2.6.3. Anti-cancer Procedure or Surgery

Prior anti-cancer procedure or surgery are defined as those taken by the patient prior to the administration of study drug. Subsequent anti-cancer procedure or surgery are defined as those taken by the patient after the discontinuation of the study drug.

In addition to the overview summary, prior and subsequent anti-cancer procedure or surgery will be coded to SOC and PT using MedDRA 27.1 or higher.

The prior anti-cancer procedure or surgery will be summarized by presenting the number and percentage of patients by SOC and PT. Patients taking the same medication multiple times will only be counted once for that PT or SOC. Each summary will be ordered by descending order of incidence of SOC to total column and PT within each SOC. If the frequencies tie, an alphabetic order will be applied.

Similarly, the subsequent anti-cancer procedure or surgery will be summarized by SOC and PT.

All prior and subsequent anti-cancer procedure or surgery will be presented in a by-patient listing.

5.2.7. Prior and Concomitant Medications

Prior and concomitant medications (CMs) are coded to Anatomical Therapeutic Classification (ATC) therapeutic group (i.e., ATC Level 2) and PT using the WHO-DD Version September 2024 or higher.

Medications taken and stopped prior to the first dose of study treatment are denoted “Prior”. Medications taken prior to the first dose of study treatment and continuing beyond the first dose of study treatment, or those medications started on or after the first dose of study treatment but no later than 30 days after the last dose or the start of a subsequent anti-tumor therapy (whichever comes first) are denoted “Concomitant”. Medication with start date/time being partially or completely missing will be assumed to be concomitant if it cannot be shown that the medication did not occur during the treatment period.

The prior medications will be summarized by presenting the number and percentage of patients by PT and ATC on safety analysis set. Patients taking the same medication multiple times will only be counted once for that PT or ATC. Each summary will be ordered by descending order of incidence of ATC and PT within each ATC. If the frequencies tie, an alphabetic order will be applied.

Similarly, the concomitant medications will be summarized.

All prior and concomitant medications will be presented in a by-patient listing.

5.2.8. Prior and Concomitant Procedures

Procedures or surgeries that occurs prior to the first dose of study treatment are denoted “Prior”. Procedures or surgeries that occurs on or after first dose date but no later than 30 days after the last dose or the start of a subsequent anti-tumor therapy (whichever comes first) are denoted “Concomitant”.

Prior and concomitant procedures or surgeries will be classified using the MedDRA version 27.1 or higher.

The prior and concomitant procedures or surgeries will be summarized by presenting the number and percentage of patients by PT and SOC on safety analysis set. Patients having the same procedure or surgeries multiple times will only be counted once for that PT or SOC. Each summary will be ordered by descending order of incidence of SOC according to total column and PT within each SOC. If the frequencies tie, an alphabetic order will be applied.

All concomitant procedures or surgeries will be presented in listing.

5.2.9. Efficacy Analyses

All efficacy analyses will be based on the efficacy analysis set. The response evaluable analysis set will be used to conduct sensitivity analysis for tumor response.

No formal comparison or hypothesis testing is planned for this study. Two-sided 95% confidence intervals (CIs) will be calculated in the applicable summary, unless otherwise specified.

Main efficacy analysis will be repeated by IDH naïve and treated status based on efficacy analysis set.

All efficacy data will be listed.

5.2.9.1. BOR, Composite CRs, ORR, CBR

The relevant response endpoints are defined in [Section 4.2.2](#). The number and percentage of patients in each category of derived BOR (CR, CR_{MRD}., CR_i, CR_h, MLFS, PR, SD, PD and NE, with reasons being NE) will be summarized. The CR rate by 24 weeks, cCR-1 rate by 24 weeks, cCR-2 rate by 24 weeks, and cCR-3 rate by 24 weeks, ORR, and CBR will be summarized with the two-sided 95% exact confidence intervals (CIs) calculated using the Clopper-Pearson exact method.

The response evaluable analysis set will be used to conduct sensitivity analysis for the above tumor response endpoints.

Swimmer plot will be presented for the treatment duration and tumor responses, including length of treatment duration, timepoint response, death.

All tumor evaluation related data will be presented in listings.

5.2.9.2. DoCR/DoOR, EFS, PFS, and OS

For the time to event endpoints, such as various DoCRs/DoOR defined in [Section 4.2.3](#), EFS and EFS for patients with CR by 24 weeks (if data allowed) defined in [Section 4.2.5](#), OS defined in [Section 4.2.6](#), and PFS defined in [Section 4.2.7](#), the 25%, 50% (median), and 75% percentile of time-to-event will be estimated using Kaplan-Meier method with their corresponding 95% CI which are calculated from a log-log transformation based on the method by [Brookmeyer and Crowley \(1982\)](#). For PFS and OS, additionally, estimates will be provided for the survival probability along with their 95% CIs which are calculated using linear transformation based on the

method by [Brookmeyer and Crowley \(1982\)](#) at selected landmarks, for example, at 3, 6, 9, 12, and 18 months. The Kaplan-Meier plots will be produced for PFS and OS.

The duration of follow-up for PFS will be summarized by reversed Kaplan-Meier method (i.e. using different censoring rule which reverses censoring indicator of PFS, i.e. patients who progressed or died in PFS analysis will be censored at the date of progression or death, patients who are censored in PFS analysis will be assigned indicator of “event” with the same duration for PFS.) to calculate median, first and third quartiles and 95% CIs. The duration of follow-up for DoCR/DoOR, EFS, OS will be summarized similarly.

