2.3.2. Dose Expansion Part

To better describe the safety of the recommended single-dose of HMPL-306 for future studies, approximately 10 AML patients are expected to be treated with HMPL-306 at this part. For a given adverse event (AE) with a true rate of 10%, 5%, or 1%, the probability of observing at least 1 AE in 10 patients is 65%, 40%, and 9.6%, respectively.

Assuming that the true complete response (CR) rate is 20%, then the probability that at least 1 case of CR is observed in a cohort of 10 patients is 89%, the probability that at least 2 cases of CR are observed is 62.4%, and the probability that no CR is observed is 11%. If further evaluation of safety and efficacy signals is warranted, then more patients may be enrolled in the dose expansion cohort.

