4.2.5. Event-free Survival

Event-free survival (EFS) is defined as the time from date of first study drug administration from Cycle 1 in continuous cycle (i.e. not from the date of single oral dose from the PK week for the dose escalation part) to treatment failure, relapse from CR (including CR_{MRD}-, CR, CRh and CRi), or death due to any cause, whichever occurs first. EFS analysis will take competitor Ivosidenib Phase III EFS definition and censoring rules as reference ([Xu et al, 2020](#)). Treatment failure is defined as failure to achieve CR (including CR_{MRD}-, CR, CRh and CRi) by Week 24. Subjects who do not achieve CR (including CR_{MRD}-, CR, CRh and CRi) by Week 24 will be considered to have had an event at Day 1 of first study drug administration from Cycle 1 (i.e. not from the date of single oral dose from the PK week for the dose escalation part). For the remaining CR responders (including CR_{MRD}-, CR, CRh and CRi), the event time will be the time of either disease relapse or death due to any cause, whichever occurs first. A response of CR (including CR_{MRD}-, CR, CRh and CRi) represents both disease control and establishment of hematopoiesis in subjects with AML and is an important predictor of OS ([Dombret et al, 2015](#)). Event-free survival will be censored upon initiation of a subsequent anticancer therapy.

The outcome (event or censor), type of event and the date of event or censoring to be considered for the EFS are presented in [Table 4](#).

Table 4 Outcome and Event or Censoring Dates for EFS

Rule	Situation	Date of Event or Censoring	Outcome
1	CR by 24 weeks ^a then relapse between scheduled visit or after one missing tumor assessment visit	Date of relapse	Event (relapse)
2	CR by 24 weeks ^a then death (no relapse) between scheduled visit or after one missing tumor assessment visit	Date of death	Event (death)
3	On treatment \geq 24 weeks without CR by 24 weeks ^a	Date of first administration of study treatment	Event (TF, on treatment \geq 24 weeks without CR)
4	Treatment discontinuation prior to 24 weeks, without CR by 24 weeks ^a	Date of first administration of study treatment	Event (TF, treatment discontinuation prior to 24 weeks without CR)
5	On treatment $<$ 24 weeks without CR and active in study	Date of the last adequate disease assessment	Censored

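### EFS dates every treatment failure at Day 1 but is summarised by quartiles with no landmark probability or curve, so its median, and often all three quartiles, will fall on Day 1

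*SAP*

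**What the plan says.** EFS is a listed secondary endpoint (SAP Table 1; Protocol Table 3). SAP 4.2.5 defines failure on a composite: "Treatment failure is defined as failure to achieve CR (including CR_{MRD}-, CR, CRh and CRi) by Week 24". It then dates that failure at the start of treatment: patients without this response "by Week 24 will be considered to have had an event at Day 1 of first study drug administration from Cycle 1". Table 4 Rules 3 and 4 apply this both to patients still on treatment at 24 weeks and to those who stopped earlier. Rule 5 censors patients on treatment for under 24 weeks, without CR and still active. Rule 9 censors, at first dose, patients with no adequate baseline or post-baseline assessment.

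For the time-to-event endpoints, EFS included, SAP 5.2.9.2 states that "the 25%, 50% (median), and 75% percentile of time-to-event will be estimated using Kaplan-Meier method". The list covers "EFS and EFS for patients with CR by 24 weeks (if data allowed"), so a responder-only analysis is also planned, conditionally. Landmark probabilities follow in a sentence that opens "For PFS and OS, additionally, estimates will be provided for the survival probability", and "The Kaplan-Meier plots will be produced for PFS and OS". Reverse Kaplan-Meier follow-up is planned for EFS. SAP 5.2.9.1 separately reports the cCR-1 rate by 24 weeks, which uses the same composite, with an exact 95% CI.

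The only response rate assumed is in SAP 2.3.2: "Assuming that the true complete response (CR) rate is 20"%. It is for CR, in a part where "approximately 10 AML patients are expected to be treated with HMPL-306".

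**The concern.** Under this definition the EFS curve drops on Day 1 by roughly the share of treatment failures. Everything it shows afterwards concerns patients who reached remission and then relapsed, died or stayed event-free. That later part is what EFS adds to a response rate. A quartile sees it only if the curve is still above the matching level after the Day 1 drop. In a relapsed or refractory population where a minority respond, the median and possibly the upper quartile will sit on Day 1 and say only that fewer than half, or fewer than a quarter, responded. The cCR-1 rate already says this more precisely. What would go unreported is the probability, among all treated patients, of having reached remission by Week 24 and being event-free at a later date.

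**Working it through.** **The plan's own figures.** With n = 10 and CR rate 0.20 (SAP 2.3.2): P(at least 1) = 1 − 0.8^10 = 0.893; P(at least 2) = 0.624; P(none) = 0.107. The SAP's 89%, 62.4% and 11% reproduce.

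**Day 1 in months.** SAP 4.2.5 gives no EFS formula. Using the PFS and OS form, (date − start + 1)/30.4375, a Day 1 event is 1/30.4375 = 0.033 months. SAP 5.1.1 shows derived variables to one decimal place, so it prints as 0.0.

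**When a quartile is Day 1.** With N patients and F events at Day 1, S(Day 1) = 1 − F/N. Patients censored on Day 1 still count in N.
- 25th percentile is Day 1 if F/N ≥ 0.25
- median is Day 1 if F/N ≥ 0.50
- 75th percentile is Day 1 if F/N ≥ 0.75

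If software averages when S equals the level exactly, read these as strict inequalities.

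**Worked cases, N = 10.**

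| Responders | Censored (Rule 5 or 9) | Day 1 events | S(Day 1) | Quartiles on Day 1 |
|---|---|---|---|---|
| 2 | 0 | 8 | 0.20 | all three |
| 3 | 0 | 7 | 0.30 | 25th, median |
| 2 | 1 | 7 | 0.30 | 25th, median |
| 2 | 4 (Rule 9) | 4 | 0.60 | 25th only |

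**How likely this is, N = 10, no Rule 5 or 9 censoring.** All three quartiles collapse with 2 or fewer responders; the median is Day 1 with 5 or fewer (4 or fewer if ties are averaged). The plan gives no rate for the EFS composite, so a range is assumed.

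| True composite rate | P(all three on Day 1) | P(median on Day 1) | Median, ties averaged |
|---|---|---|---|
| 20% | 0.678 | 0.994 | 0.967 |
| 25% | 0.526 | 0.980 | 0.922 |
| 30% | 0.383 | 0.953 | 0.850 |
| 40% | 0.167 | 0.834 | 0.633 |

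**Actual reporting groups.** The footnote to SAP Table 13 says one patient entered the expansion part and is merged into Cohort 8. The 10-patient group is therefore illustrative. Efficacy is shown by dose level (SAP 5.1.1), with at least 3 patients each, extendable to 12 (Protocol 4.1.1). At a 20% composite rate, P(all three on Day 1) is 0.8^3 = 0.512 at n = 3 (no responders), 0.655 at n = 6 (at most 1), and 0.795 at n = 12 (at most 3; 0.558 if ties are averaged).

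**How common Rule 9 might be.** The first scheduled post-baseline assessment is at 8 weeks. If survival were exponential with the 1.5-month median that Protocol 2.3.1 quotes for refractory AML (an assumption), 1 − 2^(−(56/30.4375)/1.5) = 0.57 would die before Day 56. A patient who stops early with no post-baseline assessment meets both Rule 4 (event at Day 1) and Rule 9 (censored at Day 1). Table 5 ranks censoring reasons among themselves but does not say which of these two rules prevails.

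**The case against.** The strongest reply is that the information is largely planned already. Apart from Rule 5 and 9 censoring, full-population EFS equals the 24-week composite response rate multiplied by event-free survival among those responders. The first factor comes with an exact CI; the second is covered by EFS in 24-week responders and by the duration of cCR-1. A swimmer plot and full listings are also planned. Protocol 9.2.7 likewise restricts landmarks and plots to PFS and OS, a Day 1 median is a correct result under the definition, and nothing is tested. At n = 3, full collapse means no responders, and every landmark would then be zero as well.

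Much of this stands, and it keeps the point minor. It does not close the gap. The responder analysis depends on the data allowing it and is again given as quartiles, and the two factors are never combined into an estimate with an interval. PFS landmarks answer a different question: a patient with stable disease and no remission is progression-free for PFS but a Day 1 failure for EFS. Protocol 9.2.7 contains no EFS definition; the Day 1 rule appears only in the SAP.

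Three stronger readings are tempting and unsupported:
- A reader might infer that at the plan's 20% rate all three quartiles must be one day. The 20% is for CR, whereas EFS also counts CRh and CRi. Sampling variation and Rules 5 and 9 can each move the 75th percentile off Day 1.
- A reader might infer that full-population quartiles are the only EFS output. SAP 5.2.9.2 also plans responder EFS and reverse Kaplan-Meier follow-up.
- A reader might infer that durability is never assessed. It is assessed, but only conditionally on response.

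**Conclusion.** The point holds in a limited form. The full-population EFS median will be Day 1 in any group where about half or more are Day 1 events, which is likely across the assumed composite rates of 20% to 40%. Collapse of all three quartiles needs about 75% or more Day 1 events; it is likely below a composite rate of about 25%, though not certain, and becomes unlikely by 40%. The 20% in SAP 2.3.2 serves only as a lower bound for the composite, and only if those CRs occur by Week 24. The probabilities assume independent patients and no Rule 5 or 9 censoring; such censoring makes collapse less likely. Whatever the rate, the plan names no EFS landmark probability and no EFS curve, so the all-patient probability of reaching remission and remaining event-free is not estimated. Priority is minor: EFS is one of several secondary activity endpoints in a phase 1 study with no formal hypothesis test.

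**What to change.** In SAP 5.2.9.2, add EFS to the sentence on landmark probabilities with 95% CIs (for example at 6, 9 and 12 months) and to the sentence on Kaplan-Meier plots. Tabulate EFS events by the types Table 4 already labels: treatment failure, relapse and death. Keep the quartiles, which are most useful for the 24-week responder subset. When editing Table 4, state which of Rules 4 and 9 prevails when both apply, since the height of the Day 1 step depends on it.

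The cost is a few more table shells, with no new data or endpoint. Intervals will be wide. For a landmark estimate of 0.20 with n = 10 and no censoring, the standard error is √(0.2 × 0.8/10) = 0.126, and the linear interval already specified for PFS and OS runs from −0.05 to 0.45. A transformation that respects the 0 to 1 range would be tidier, but that choice is secondary.
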